16.2.2 Criteria for Handling Patient Data

The criteria for handling patient data are described below.

The sponsor, in collaboration with the medical specialists, will determine the approach to handle data if there are problematic patients for handling except the criteria listed below:

(1) Handling of missing values and abnormal values

- No specific measures will be implemented. Analyses will be performed using all the data gathered for each time frame. For each analysis proportions will be estimated on the basis of the whole population analyzed.
- The analyses will include all data points unless the laboratory tests, such as the effect of hemolysis during blood collection, showed obvious abnormal values. In the presence of excluding abnormal laboratory results from analysis, these values will still be provided and the reasons for exclusion clearly stated.

(2) Patients with violations of study drug randomization

- For those analyses involving the AT population, the data of patients who have been administered study drug of different treatment arm from allocated treatment arm will be treated as that arms based on actual administered study drug.
- In the analyses for FAS or TR population, data will be treated as allocated treatment arm.

16.3 Statistical Methods

The main statistical methods to evaluate the primary and secondary objectives of the trial are described below.

All the details of the analyses performed in the trial are described in the statistical analysis

plan and a report analysis plan will be separately developed.

16.3.1 Patient Disposition, Baseline and Treatment Characteristics

(1) Patient Disposition

The number of patients included in each population, the reasons for exclusion, and any randomization and/or stratification errors will be summarized schematically.

(2) Patient Baseline Characteristics

The distribution of data such as main patient background characteristics, disease characteristics, and baseline laboratory values will be summarized.

(3) Evaluation of Comparability

Deviation between study drugs will be evaluated using the appropriate statistical test depending on the characteristics of the data.

16.3.2 Primary Endpoint Analyses

Main methods of primary endpoint (OS) analysis are shown below.

(1) Primary analysis

- OS in the FAS will be compared between the two study treatment arms using stratified log-rank test by three stratification factors (significance level is 5% for 2 sided test). 0.305% and 4.899% are set at the time of second interim and main evaluation respectively by alpha spending function with O'Brien-Fleming form and considering correlation between each test statistic to maintain significance level throughout the study less than or equal to 5%. Superiority of efficacy of TAS-118/L-OHP arm to S-1/CDDP arm is statistically considered valid when either p-values are less than or equal to each significance level in each statistical test. Also, a confirmation of the superiority in the first interim analysis will not be done.

(2) Sensitivity analyses of primary analysis

- OS in the FAS will be compared between the two study treatment arms using unstratified log-rank test. In addition, Cox Proportional Hazard (CPH) model will be performed with the study drug as covariate.

(3) Secondary analysis of primary endpoint

Following analyses will be performed in FAS population.

- Hazard ratio of OS with 95% confidence interval will be estimated by CPH model with the study drug and three stratification factors as covariates.
- In each study treatment, survival curves of OS will be estimated and Median Survival Time (MST) with 95% confidence interval using the Kaplan-Meier method will be presented. Otherwise the number at risk and cumulative event free rate every three months will be presented.

- In each stratification factor and each study treatment, survival curves of OS will be estimated and MST with 95% confidence interval using the Kaplan-Meier method will be presented. Otherwise the number at risk and cumulative event free rate every three months will be presented.

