1.1 Title of Protocol, Protocol Number and Date of Preparation

Title of study: An open-label randomized multi-center phase III study of TAS-118 plus Oxaliplatin versus S-1 plus Cisplatin as first-line therapy in patients with advanced gastric cancer

Protocol number: [REDACTED] (Ver.P05)

Date: 07 Nov 2019

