16.1.1 Interim Analyses

The Independent Data Monitoring Committee (IDMC) will perform two interim analyses. In order to evaluate the safety data, first interim analysis will be performed by the IDMC. At second interim analysis, the IDMC will evaluate the safety and efficacy data based on these analyses. The IDMC will propose whether the trial should stop earlier based on the results obtained to that point. Further details of the role and responsibility of IDMC and the review process are provided in the IDMC charter. The interim analyses will be performed with the data gathered up to following cutoff point.

(1) Data cutoff for the first interim analysis

- In safety analyses, the cutoff data will be defined on the basis of the date when 100 death events are confirmed.

(2) Data cutoff for second interim analysis

- The cutoff date for primary endpoint is the date when 219 death, which is the 50% required number of death events, are confirmed.
- In safety analyses, the cutoff data will be defined on the basis of the date when 219 death events are confirmed.

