16.1.2 Primary Evaluation

The primary analysis will be performed when the cutoff date is determined, and CRFs, dispositions and adoptions of all patients are fixed again.

(1) Data cutoff for primary evaluation

- The cutoff date for primary endpoint will be set at the date when 491 death events are confirmed, representing the final number of events required.
- In safety analyses, the cutoff data will be defined on the basis of the date when 491 death events are confirmed.

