16.4 Determination of Sample Size

Number of target patients: 686 subjects

(TAS-118/L-OHP arm: 343 subjects, S-1/CDDP arm: 343 subjects)

Number of target patients as FAS: 650 subjects

(TAS-118/L-OHP arm: 325 subjects, S-1/CDDP arm: 325 subjects)

In a randomized phase II study of S-1/LV therapy, S-1/LV/L-OHP therapy, and S-1/CDDP therapy in patients with unresectable, advanced, recurrent gastric cancer (██████████), MST of the S-1/LV/L-OHP therapy was 18.4 months and MST of S-1/CDDP therapy was 12.6 months, respectively. In SOS trial which conducted in Japan and Korea,

MST of the S-1/CDDP (5-week-interval administration) was 13.9 months, although the Japanese subgroup showed an MST of 15.5 months. Taking the difference on the ratio of target number of randomized patient between Japan and Korea and on the target population in this trial into consideration, MST of the S-1/CDDP is assumed to be 14.5 months for this trial and MST of TAS-118/L-OHP is set 19.33 months (hazard ratio : 0.75).

In the condition that MST is exponentially distributed and 2-sided 4.899% significance level and 85% power, the required number of death events is 437 for logrank test in the primary analysis which compares OS of TAS-118/L-OHP arm with of S-1/CDDP for primary evaluation. In the case that patients are uniformly enrolled in accrual period of 19 months and follow-up period is 19 months, the total required number of patients can be estimated 686 including expectation of 5% exclusion from FAS. Patients can be additionally enrolled when the number of events is less than expectation in the evaluation during the trial. The sponsor will determine, in collaboration with the statistics advisor, the final number of patients if the number of patient increases.

Null and alternative hypotheses of statistical test are as follows

Null hypothesis $H_0 : \lambda_T / \lambda_C = 1$

Alternative hypothesis $H_1 : \lambda_T / \lambda_C \neq 1$

λ_C : Hazard of S-1/CDDP arm

λ_T : Hazard of TAS-118/L-OHP arm

Powers at various situations where expected MSTs of each arm change are shown in Table 16.4-1.

Table 16.4-1 Powers(%) at various situations where expected MSTs of each arm change

		MST of S-1/CDDP arm						
		12	13	14	14.5	15	16	17
MST of TAS-118/L-OHP arm	17	95.3	79.8	52.4	38	25.4	9.1	2.4
	18	98.8	92.4	74.5	61.5	47.5	23	8.5
	19	99.8	97.7	88.9	80.4	69.2	43.2	21
	19.33	99.9	98.5	92	85	75.2	50.3	26.6
	20	100	99.4	96.1	91.8	85	64.2	39.4
	21	100	99.9	98.8	97.1	93.9	80.9	59.5

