	22	100	100	99.7	99.2	97.9	91.3	76.6

Note: Powers are estimated in the condition that the number of death events are 437 and 2-sided significance level is 4.899%. The underline is the power set in this trial.

17. Case Report Form

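### The April 2017 change from 437 to 491 deaths was not carried through the protocol, and neither document gives the hazard ratio or power behind 491.

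*Protocol*

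**What the plan says.** The protocol is the version marked "Date: 07 Nov 2019". On the number of deaths and the success rule it says:

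- **16.1.2:** the primary cutoff is the date when "491 death events are confirmed, representing the final number of events required".
- **16.4:** "the required number of death events is 437 for logrank test in the primary analysis", with 85% power at hazard ratio 0.75. The note to Table 16.4-1 says "Powers are estimated in the condition that the number of death events are 437 and 2-sided significance level is 4.899" per cent, and identifies the underlined 85% as the power set for the trial.
- **16.1.1:** the second interim cutoff is "the date when 219 death, which is the 50% required number of death events, are confirmed".
- **16.3.2:** "0.305% and 4.899% are set at the time of second interim and main evaluation respectively by alpha spending function", so that the overall level stays at or below 5%. Superiority is "statistically considered valid when either p-values are less than or equal to each significance level in each statistical test".
- **16.3:** "All the details of the analyses performed in the trial are described in the statistical analysis" plan.

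The SAP agrees on 491 deaths (2.1.3, Table 4-1, 5.1.1.1) and keeps the two designs apart. Its 437-death calculation (2.1.2) is headed as preceding study initiation. Table 4-1 labels 0.305% and 4.899% as levels at sample size determination, and section 4 says they will be recalculated, with code in 5.2.4.12. Section 2.1.3 reports that the IDMC met in March 2017 and recommended 491 because newly available drugs might prolong OS and reduce power. The protocol was revised on 12 April 2017. No hazard ratio, medians or power is given for 491. SAP 1.3, which lists changes from the protocol, mentions only the FAS definition.

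**The concern.** Two sections of one protocol version give different required numbers of deaths for the same analysis, and nothing marks 437 as the original design. The figures that depend on 437 were left in place: the 50% fraction, the 4.899% final level, the claim that this level controls alpha, and the power table.

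Two things are at stake. First, the protocol's numerical success rule differs slightly from the SAP's, and its alpha statement is not true of a 491-death analysis. Second, the only powers stated (85% for the final test, 85.1% overall) belong to an analysis that will not be run. SAP 2.1.3 itself doubts the assumption behind them, so a reader cannot tell what effect the 491-death analysis was meant to detect, or with what power. The missing basis matters more because the IDMC that recommended 491 was also the body that evaluated efficacy at the second interim, cut on 30 November 2016. Nothing in the documents suggests that the change depended on interim results, but a stated external basis would let readers see that it did not.

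**Working it through.** **Inputs.** Overall alpha 5% two-sided; levels 0.305% and 4.899% (protocol 16.3.2; SAP 2.1.2 gives z = 2.9627 and 1.9687); information fraction 0.5 (SAP 2.1.2); hazard ratio 0.75, 85% power and 437 deaths (protocol 16.4); 1:1 allocation; interim at 219 and final at 491 deaths. Information is taken as deaths/4. The SAP code uses the observed stratified log-rank variance, so the levels below are expected values.

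**1. The original design reproduces.**

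- Deaths = 4(z + z_power)²/(ln HR)² = 4(1.9687 + 1.0364)²/(0.2877)² = 436.5, so 437.
- Power = Φ(−ln HR·√d/2 − z) = 85.0% at 437 deaths; 85.1% overall with the interim.
- O'Brien-Fleming-type spending at fraction 0.5 gives z = 2.9626 and 1.9686 (0.305% and 4.900%; the plan's 4.899% is a truncation).
- All 49 cells of Table 16.4-1 reproduce within 0.05 points at 437 deaths.

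The old figures are therefore correct for the old design.

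**2. Information fraction.** 219/437 = 50.1%; 219/491 = 44.6%.

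**3. Alpha at 219/491.** The correlation of the two statistics is √(219/491) = 0.668.

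| Rule | Result, two-sided |
|---|---|
| Fixed 0.305% and 4.899%: total alpha spent | 5.020% |
| Final level holding 5%, 0.305% already spent | 4.878% (z = 1.9705) |
| Final level holding 5%, 0.309% spent (fraction 219/437) | 4.876% |
| Final level, information fraction 0.42 to 0.47 | 4.868% to 4.888% |

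The protocol and SAP rules disagree only for a final p-value between about 4.878% and 4.899%. That adds about 0.02 percentage points to the chance of success under the null and 0.03 at hazard ratio 0.75.

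**4. Power at 491 deaths and 4.878%.** At hazard ratio 0.75: Φ(0.2877 × √491/2 − 1.9705) = 88.8%, or 88.9% overall with the interim.

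| True hazard ratio | Final-test power |
|---|---|
| 0.75 | 88.8% |
| 0.77 | 82.3% |
| 0.78 | 78.3% |
| 0.80 | 69.2% |

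Power of 80%, 85% and 90% corresponds to hazard ratios of 0.776, 0.762 and 0.746. The largest observed hazard ratio that reaches significance, exp(−2z/√d), moves from 0.828 at 437 deaths to 0.837 at 491.

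**5. Can the basis for 491 be inferred?** No. At hazard ratio 0.75 and 4.899%, 85% power needs 437 deaths and 90% needs 511, so 491 is not a move to 90%. At least two assumption sets, neither of them in the documents, give 491. Medians of 15.5 and 20.33 months (one month added to each) at 85% power give 490.9. Medians of 15 and 19.33 months at 80% power give 491.2.

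**6. SAP code.** Section 5.2.4.12 still uses hazard ratio 0.75 and beta 0.15, giving maximum information ((1.9686 + 1.0364)/ln 0.75)² = 109.1, about 436 deaths. The 491-death equivalent is 491/4 = 122.75.

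**The case against.** The strongest reply is that the SAP already governs. Its Table 3-1 takes interim information as an input to the final level, section 4 says the levels will be recalculated, and 5.2.4.12 gives the code. Protocol 16.3.2 derives its levels from a spending function, so it can be read as a method with design-stage values, and 16.3 leaves the detail to the SAP. On alpha this largely stands: the planned SAP test is not inflated. But a general referral does not cancel an explicit numerical rule in the section that defines success, and SAP 1.3 does not disclose the difference.

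Other points also stand in part. The 50% was accurate when the interim was cut, before the amendment, and no remaining decision turns on it. The note to Table 16.4-1 states its 437-death condition; what is missing is a label saying that this is the original design. Section 16.4 still explains correctly where 686 patients came from. The numerical basis for 491 may exist in IDMC material outside these documents, so the claim is only that the protocol and SAP do not state it.

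A further objection is that printing 88.8% at hazard ratio 0.75 features the very assumption that SAP 2.1.3 doubts. That is a fair warning. The added powers must be headed as conditional and must not be presented as the rationale for 491.

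**Conclusion.** The concern holds; it should be fixed, with high confidence. This is an incomplete amendment and not an arithmetic error. The current protocol gives two required event counts, and it attaches a success level and an alpha statement to a 491-death analysis for which they were not derived. The alpha consequence is about 0.02 percentage points, assuming information proportional to deaths and 0.305% spent at the interim, and the SAP's recalculation deals with it. The more important gap is that no effect size or power is stated for the analysis that will be run. Depending on the true hazard ratio, final-test power at 491 deaths runs from 88.8% (at 0.75) to 69.2% (at 0.80).

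**What to change.** 1. **Protocol 16.3.2:** replace the fixed 4.899% with the final level recalculated by the O'Brien-Fleming-type spending function from the alpha already spent and the observed information (SAP section 4 and 5.2.4.12). Label 0.305% and 4.899% as design-stage values, and give about 4.88% as an expected value only.
2. **Protocol 16.4:** label 437 deaths, 85% power and Table 16.4-1 as the original design that gave 686 patients. Add that, with 491 deaths and a hazard ratio still at 0.75, power is 88.8% for the final test (88.9% overall), and that the final test has 85% power at 0.762. Add the table below, headed as conditional final-test powers and not as the target behind 491.
3. **Protocol 16.1.1:** note that 219 was 50% of the 437 deaths then required and is 44.6% of 491.
4. **SAP 2.1.3:** the sponsor states the assumption on which 491 was based, with the conditional powers beside it.
5. **SAP 5.2.4.12:** comment that beta 0.15 and the resulting maximum information (109.1, about 436 deaths) belong to the original design.

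Power (%) at 491 deaths and two-sided 4.878%; rows are the TAS-118/L-OHP median and columns the S-1/CDDP median, in months:

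| | 12 | 13 | 14 | 14.5 | 15 | 16 | 17 |
|---|---|---|---|---|---|---|---|
| 17 | 97.1 | 84.2 | 57.2 | 41.8 | 28.0 | 9.7 | 2.4 |
| 18 | 99.4 | 94.9 | 79.2 | 66.5 | 52.0 | 25.3 | 9.1 |
| 19 | 99.9 | 98.7 | 92.1 | 84.7 | 74.2 | 47.3 | 23.0 |
| 19.33 | 100 | 99.2 | 94.6 | 88.8 | 79.9 | 54.9 | 29.2 |
| 20 | 100 | 99.7 | 97.6 | 94.4 | 88.8 | 69.2 | 43.3 |
| 21 | 100 | 100 | 99.4 | 98.4 | 96.1 | 85.1 | 64.5 |
| 22 | 100 | 100 | 99.9 | 99.6 | 98.8 | 94.0 | 81.2 |

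The cost is wording in three protocol subsections, one table, one or two sentences in the SAP and one code comment. The endpoint, population, test, event target, sample size and SAP testing procedure do not change.

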16.3.3 Secondary Endpoints Analyses

Main methods of secondary endpoints analyses are shown below.

16.3.3.1 Efficacy Endpoints

(1) Overall Response Rate (ORR)

Following analyses will be performed in TR population.

- In each study treatment, best overall responses will be summarized and ORRs with 95% confidence interval will be estimated. The treatment comparison will be done using Fisher's exact test.
- In each study treatment, onset date, duration of response (duration of overall response and duration of overall complete response) for antitumor effect will be summarized in patients with responses.

(2) Disease Control Rate (DCR)

- In each study treatment and TR population, DCR based on the best overall response will be estimated. The treatment comparison will be done by Fisher's exact test.

(3) Progression Free Survival (PFS)

- In each study treatment and FAS population, survival curves of PFS will be estimated and MST with 95% confidence interval using the Kaplan-Meier method will be presented. Otherwise the number at risk and cumulative event free rate every three months will be presented.
- PFS in the FAS will be compared between the two study treatment arms using stratified log-rank test by three stratification factors. In addition, hazard ratio of PFS with 95% confidence interval will be estimated by CPH model with the study drug as covariates.

(4) Time to Treatment Failure (TTF)

- In FAS population, TTF analyses will be performed by the same ways as PFS analyses.

16.3.3.2 Treatment Status

(1) Treatment discontinuation

- For each study treatment and FAS population, treatment discontinuations and their reasons will be summarized.

(2) Dose Intensity

- For each study treatment and FAS population, actual dose intensity and relative dose intensity of each patient will be summarized.

16.3.3.3 Safety Analyses

Following analyses will be performed in AT population. However, same analyses will be done in FAS population if AT population doesn't correspond to FAS population.

(1) Adverse event

- Rate of adverse event will be summarized.
- For maximum grade of each adverse event in each patient, the number of patient and rate of adverse event by grade will be summarized.
- For all adverse events between onset of study drug administration and end of the trial, tables of their class, grade, onset date, causal relationship, outcome and treatment contents will be described.

(2) Adverse drug reaction

- For adverse drug reaction, same analyses as adverse events will be performed.

(3) Laboratory test

- Transition of main hematological laboratory values (White Blood Cell, Lymphocyte, Neutrophil, Hemoglobin, Platelet) at each point of each patient will be described as graph.

(4) Clinical findings

- For clinical findings (stomatitis, anorexia, diarrhea, peripheral sensory neuropathy), onset date of each patient, date of occurrence for maximum grade, first date of condition with grade 3 or higher, and time to recovery will be presented as list in each study treatment arm.

16.4 Determination of Sample Size

Number of target patients: 686 subjects

(TAS-118/L-OHP arm: 343 subjects, S-1/CDDP arm: 343 subjects)

Number of target patients as FAS: 650 subjects

(TAS-118/L-OHP arm: 325 subjects, S-1/CDDP arm: 325 subjects)

In a randomized phase II study of S-1/LV therapy, S-1/LV/L-OHP therapy, and S-1/CDDP therapy in patients with unresectable, advanced, recurrent gastric cancer (██████████), MST of the S-1/LV/L-OHP therapy was 18.4 months and MST of S-1/CDDP therapy was 12.6 months, respectively. In SOS trial which conducted in Japan and Korea,

MST of the S-1/CDDP (5-week-interval administration) was 13.9 months, although the Japanese subgroup showed an MST of 15.5 months. Taking the difference on the ratio of target number of randomized patient between Japan and Korea and on the target population in this trial into consideration, MST of the S-1/CDDP is assumed to be 14.5 months for this trial and MST of TAS-118/L-OHP is set 19.33 months (hazard ratio : 0.75).

In the condition that MST is exponentially distributed and 2-sided 4.899% significance level and 85% power, the required number of death events is 437 for logrank test in the primary analysis which compares OS of TAS-118/L-OHP arm with of S-1/CDDP for primary evaluation. In the case that patients are uniformly enrolled in accrual period of 19 months and follow-up period is 19 months, the total required number of patients can be estimated 686 including expectation of 5% exclusion from FAS. Patients can be additionally enrolled when the number of events is less than expectation in the evaluation during the trial. The sponsor will determine, in collaboration with the statistics advisor, the final number of patients if the number of patient increases.

Null and alternative hypotheses of statistical test are as follows

Null hypothesis $H_0 : \lambda_T / \lambda_C = 1$

Alternative hypothesis $H_1 : \lambda_T / \lambda_C \neq 1$

λ_C : Hazard of S-1/CDDP arm

λ_T : Hazard of TAS-118/L-OHP arm

Powers at various situations where expected MSTs of each arm change are shown in Table 16.4-1.

Table 16.4-1 Powers(%) at various situations where expected MSTs of each arm change

		MST of S-1/CDDP arm						
		12	13	14	14.5	15	16	17
MST of TAS-118/L-OHP arm	17	95.3	79.8	52.4	38	25.4	9.1	2.4
	18	98.8	92.4	74.5	61.5	47.5	23	8.5
	19	99.8	97.7	88.9	80.4	69.2	43.2	21
	19.33	99.9	98.5	92	85	75.2	50.3	26.6
	20	100	99.4	96.1	91.8	85	64.2	39.4
	21	100	99.9	98.8	97.1	93.9	80.9	59.5
	22	100	100	99.7	99.2	97.9	91.3	76.6

Note: Powers are estimated in the condition that the number of death events are 437 and 2-sided significance level is 4.899%. The underline is the power set in this trial.

17. Case Report Form

